7.4 Compliance

A record of the dose titration and of deviation from prescribed treatment will be kept in the patients' file and in the respective CRFs.

7.5 Concomitant Therapy

Concomitant therapy will be continued throughout the study. Drugs used as concomitant therapy and dose should be kept unchanged throughout the study whenever possible. Treatment of side effects, concurrent diseases, and dose adaptations of baseline concomitant therapy are generally allowed but have to be documented accordingly. Concomitant therapy will be documented in the patients' file and in the respective CRFs.

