- MRS (multi-voxel magnetic resonance spectroscopy)
- Neurological measures: Expanded disability status scale (EDSS), SCRIPPS neurological rating scale (SNRS), MS functional composite (MSFC) consisting of 9-HP-test (Nine-Hole-Peg Test), timed 25 foot walk, paced auditory serial addition test (PASAT), Depression scale (Hospital Anxiety and Depression Scale) and a fatigue scale (Fatigue severity scale according to Flachenecker et al.), Hamburg Relapse Assessment Scale (HARAS)
- Immunological parameters
- Biomarker assessment (Cathepsin G activity and PGE₂ levels)

Patient selection: Subjects with clinically isolated syndrome (CIS) fulfilling MRI inclusion criteria (see below) or clinically definite relapsing remitting multiple sclerosis (RRMS) in an active inflammatory phase who either failed standard treatment by clinical measures or were not eligible for any of the standard treatments (e.g. interferon beta, glatiramer acetate) or, after consultation with an independent neurologist, elected not to start or to continue with any of these treatments. Subjects will be enrolled following completion of all pre-screening procedures. After enrollment, subjects will undergo baseline Gd-enhanced MRIs at 4-week intervals prior to the first dose of study drug.

Statistical Plan: Evaluable populations

The primary outcome in the treatment phase (Stage 3) will first compare mean Gd-enhancing lesion number occurring during the 4 month baseline to mean Gd-enhancing lesion number occurring months 5, 6, 7, 8 on treatment in patients treated with a dose of at least 800 mg t.i.d.

A secondary analysis will compare mean Gd-enhancing lesion number occurring over the 4 months of baseline to that occurring during all treatment months on treatment.

Sample size

Based on analyses of a natural history cohort studied with monthly MRIs for a minimum of one year, a baseline-to-treatment designed trial incorporating 4 baseline MRIs and 4 treatment MRIs will require 30 patients to detect a 40% reduction in Gd-enhancing lesions with an alpha of 0.05 (one-sided).

2. Introduction and Study Rationale

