2.2 Known and proposed mechanisms of action of the frankincense extract and BA

Preparations from the olegum resin of *Boswellia serrata* and other *Boswellia* species have been used in traditional eastern and asian medicine from 1500 BC, but were described only in the 1980ies by Indian scientists to show anti-inflammatory potential in animal models of arthritis (1). Following these observations the induction of a broad range of immunomodulatory and antiinflammatory effects by boswellic acids (BAs) could be proven by several independent research groups (7).

Ammon and colleagues demonstrated that BAs inhibit 5-Lipoxygenase (5-LO) (8), and subsequently Werz et al. (manuscript submitted) could show that the beta-BAs inhibit the serine protease cathepsin G (Cat G) and the microsomal prostaglandin E2 synthase (mPGES)-1 specifically. The pharmacological strategy of dual inhibition of cathepsin G and mPGES-1 or even inhibition of three key enzymes in the arachidonic acid pathway by dual mPGES-1/5-LO or even triple Cat G/mPGES-1/5-LO inhibitors is novel and has thus far not been described for any compound. Importantly, in contrast to the traditionally used non-steroidal anti-inflammatory drugs (NSAIDs) and coxibs that suppress the formation of all prostaglandins by inhibition of cyclooxygenases, these new compounds selectively inhibit the formation of PGE₂ and do not inhibit the synthesis of prostacyclin, which is a prominent safety aspect. Elevated levels of PGE₂ have recently been described in the Cerebrospinal fluid (CSF) of MS patients (9). Observations of a regulatory role in the glutaminergic, neurotransmission of PGE₂ (10) are raising the question of whether BAs might even show neuroprotective effects.

The dual inhibition of 5-LO and the mPGES-1 might be a second relevant mechanism in approaching MS. The relevant classes of synthetic small molecule compounds with this mechanism of action are: indol-3-carboxylates, α -substituted pirinixic acid derivatives, and α -substituted thiophenylether derivatives. The latter two activate the peroxisome proliferators-activated receptor (PPAR)- γ , for which a multitude of activities that are beneficial in Experimental autoimmune encephalitis (EAE), the mouse model of MS, and potentially also in MS including blocking IL-12/IL-23 family members and thus Th1- and Th17 development, immune cell extravasation, NMDA-mediated excitotoxicity and others (11) have been shown.

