Cathepsin G (Cat G) participates in killing and digestion of pathogens, but is also involved in tissue remodelling at inflammatory sites by increasing matrix metalloproteinase (MMP) activity. The chemotactic activity of Cat G appears to play a role in synovial inflammation in rheumatoid arthritis via attracting neutrophils, and reduced Cat G activity is a mechanism of host immune defense evasion during tuberculosis. The chemokine CXCL5 is significantly downregulated in immunomodulatory treated MS-patients (12), and Cat G increases the activity of the CXCL5 and CCL15, which are important chemoattractants of monocytes and neutrophils (13). Cat G differentially modulates the antigen processing of myelin basic protein (MBP) in various APCs (B cells, dendritic cells) (14). Inhibition of Cat G resulted in failure to process MBP, a central autoantigen of MS (15), although the relevance of these data for MS is currently not clear to the applicants. Finally, Cat G has been shown to activate specifically pro-inflammatory cytokines IL-1 and TNF- α (16).

5-Lipoxygenase (5-LO) catalyzes two reactions in the formation of proinflammatory leukotrienes and is involved in the TNF- α -induced expression of CXCL9, CXCL10 and CXCL11, which are all ligands for the Th1 chemokine receptor CXCR3. 5-LO inhibitors downregulate CXCR3 ligands. Blocking 5-LO in wild-type mice delayed the onset and reduced the severity of EAE, but did not reduce the production of Th1- and Th17 cytokines (17). In contrast, EAE is exacerbated in constitutive knockouts of 5-LO suggesting that cell-type or tissue-specific inhibition is beneficial, but outweighed by global lack of the enzyme (18). Of particular interest here is the finding that 5-LO is among the most highly differentially expressed genes in the brains of MS patients and animals with EAE (19) and also its upregulation in the brains of patients with Alzheimer's disease (20) indicating a central role in the neuroinflammatory processes in both diseases. The latter notion is supported by the observation that 5-LO and FLAP in monocytes and microglia participate in the generation of products that are toxic for neurons (21-23). As a further indication of an involvement of 5-LO in MS, several reports have found elevated leukotriene (LTB₄) concentrations in the CSF of MS patients (24). Finally, the administration of omega-3 poly-unsaturated fatty acids lowers the expression of 5-LO (25).

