3.2 Secondary Objective

The secondary objective of this study is to determine the effect of BOSWELAN therapy on disease activity in CIS or RR multiple sclerosis as measured by MRI

activity. In addition, the effect of BOSWELAN on immunological function will be assessed.

The primary efficacy outcome measure of this study will be the mean total number and the volume of Gd-enhancing lesions based on a comparison of 4 baseline MRIs and 4 treatment MRIs (months 5-8) in patients of this study who tolerated a dose of at least 800 mg t.i.d.

Secondary outcome measures will be:

1. Number of new active lesions (new Gd-enhancing lesions plus new non-enhancing or enlarging T2 lesions). Number of persisting Gd-enhancing lesions. Number of new Gd-enhancing lesions evolving into persistent T1 hypointense lesions. T2 lesion volume (fast spin echo sequence), T1 hypointense lesion volume, Number of persisting T1 lesions, Magnetization Transfer Ratio (MTR), brain parenchymal fraction as measure of atrophy
2. Relapse rate

Tertiary outcome measures will be:

1. Magnetic resonance spectroscopy (MRS). Multivoxel magnetic resonance spectroscopy will be performed once during the baseline and twice during the treatment phase (months 4 and 8) in three patients (those with the highest EDSS).
2. Expanded disability status scale (EDSS), SCRIPPS neurological rating scale (SNRS), MS functional composite (MSFC) consisting of 9-HP-test (Nine-Hole-Peg Test), timed 25 foot walk, paced auditory serial addition test (PASAT), and in addition a depression scale (Hospital Anxiety and Depression Scale) and a fatigue scale (Fatigue severity scale according to Flachenecker), Hamburg Relapse Assessment Scale (HARAS).

Immunological measures:

A number of immunological measures will be studied to determine the in vivo immunomodulatory effect, in particular the influence on T helper 1 (Th1) and Th2 cytokines,

Biomarker assessments:

Cathepsin G and mPEGS-1 serum levels will be analyzed at every visit starting from baseline (month 0).

4. Study Outline

Months -3 - 0	Month 1	Month 2	Months 3-8	Months 9-12
Baseline MRI Lesion frequency of 0.5 or greater	Dose escalation to treatment dose Monthly MRI	Stabilization of dose Monthly MRI	Primary treatment phase Monthly MRI Assessment of individual treatment effect	Follow up of patients until Month 12 and MRI; optional for patients: washout or treatment continuation

5. Study Population

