7.5.3 Treatment of Relapses on Scheduled or Unscheduled Visits

Patients having a clinically significant relapse/exacerbation will be treated according to the recommendations of the German society for neurology (DGN) with 1000 mg methylprednisolone, given once a day via i.v. infusion for 3 days unless there are valid reasons for not treating or for alternative schedules. In case of a relapse each patient has to give written informed re-consent before continuing the study irrespective of his/her choice to receive methylprednisolone. In the case of methylprednisolone administration, a subsequent MRI examination will be postponed for at least 28 days, while treatment with BOSWELAN and study visits will be continued according to the study protocol.

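### Immunology and biomarker blood has no post-steroid interval, and PGE2 samples carry no time of last NSAID intake, so the mechanism results can mimic an absent drug effect or mask a real one

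*Protocol*

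**What the plan says.** **Outcomes.** The Summary's tertiary list has immunological parameters and, next to them, "Biomarker assessment (Cathepsin G activity and" PGE2 levels. Section 3.2 places immunological function under the secondary objective, with Th1 and Th2 cytokines singled out. For the biomarkers it says: "Cathepsin G and mPEGS-1 serum levels will be analyzed at every visit starting from baseline (month 0". The visit lists in Section 10.1 are narrower: immunology and biomarker blood appear at months 0, 1, 3, 8 and 12.

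**Steroids.** After methylprednisolone for a relapse, Section 7.5.3 postpones the MRI by at least 28 days, "while treatment with BOSWELAN and study visits will be continued according to the study protocol". Sections 9.1 and 10.1 repeat the 28 days for MRI. For blood, Section 10.1 asks only that it be drawn before steroids are taken, because steroids deplete lymphocytes.

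**Other medication.** Section 7.5 asks that drugs and doses stay unchanged where possible, then adds: "Treatment of side effects, concurrent diseases, and dose adaptations of baseline concomitant therapy are generally allowed but have to be documented accordingly". Section 7.5.2 bars the Table 2 agents other than corticosteroids; Table 2 names no NSAID or coxib. Section 7.5.4 requires all medication to be recorded from the start of study drug. Section 2.2 describes "non-steroidal anti-inflammatory drugs (NSAIDs) and coxibs that suppress the formation of all prostaglandins by inhibition of cyclooxygenases".

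**The concern.** The trial has one arm, and its mechanism claims rest on comparing a patient's on-treatment blood with that patient's month 0 blood. Anything that acts on the measured markers and is more common after month 0 will look like an effect of the study drug. Anything more common at month 0 will hide one.

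Two such exposures are open. A methylprednisolone course can fall shortly before a scheduled immunology or biomarker sample. An as-needed NSAID or coxib can be taken shortly before a PGE2 sample. The protocol recognises the steroid problem for MRI and, in part, for lymphocytes, but does not carry its 28-day rule over to blood. At stake is the reading of the mechanism data, which the protocol puts in its title and recommends for dose finding and responder profiling (Sections 2.2 and 15).

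**Working it through.** The protocol gives no figure for these outcomes, so there is none to reproduce. The check sets the rules side by side and then bounds the size on stated assumptions.

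**1. Rules around a steroid course**

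| | MRI | Immunology and biomarker blood |
|---|---|---|
| Before the course | Scan obtained first (10.1) | Draw before steroids are taken (10.1), but the mandatory relapse visit lists neither sample |
| After the course | At least 28 days (7.5.3, 9.1, 10.1) | No interval; visits continue on schedule (7.5.3) |

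The relapse visit leaves other procedures to the investigator, so a pre-steroid sample is possible but not secured.

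**2. Baseline against treatment.** The month 0 sample is shielded. Table 2 requires 8 weeks off corticosteroids. Section 5.3 delays treatment to at least 60 days after i.v. steroids when a relapse falls in the last 30 days of baseline. On-treatment samples have no equivalent, so a steroid effect falls mainly on the on-treatment side. Co-medication for side effects of the study drug can also begin only after month 0.

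**3. Chance that a course lands near a sample.** The title gives 32 weeks and the Summary 8 months of treatment, so a study month is 32/8 = 4 weeks, and the period is 32 × 7 = 224 days. Assume a course ends at a random time in it, and ignore visit windows.
- Samples at months 1, 3 and 8 (Section 10.1): 3 × 28 = 84 days lie within 28 days before a sample; 84/224 = 37.5%.
- Samples at every clinic visit (Section 3.2; months 1, 2, 3, 5, 6, 7 and 8, month 4 being by telephone): 7 × 28 = 196 days; 196/224 = 87.5%.

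The protocol states no expected number of relapses, so these are chances per course and not counts of patients.

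**4. Size of a false shift.** Let p0 and p1 be the shares of month 0 and on-treatment samples affected, and r the relative lowering of the marker in an affected sample. With an inert drug and similar underlying levels in all patients, the apparent change in the mean is

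(1 − p1·r)/(1 − p0·r) − 1.

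The documents give no value for p0, p1 or r. The range r = 0.5 to 0.8 is an assumption.

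| p0 | p1 | r = 0.5 | r = 0.8 |
|---|---|---|---|
| 0 | 0.10 | −5% | −8% |
| 0 | 0.20 | −10% | −16% |
| 0 | 0.30 | −15% | −24% |
| 0.10 | 0.20 | 0.90/0.95 − 1 = −5.3% | 0.84/0.92 − 1 = −8.7% |
| 0.20 | 0.20 | 0 | 0 |
| 0.20 | 0 | 1/0.90 − 1 = +11% | 1/0.84 − 1 = +19% |

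In the planned 30 patients, shares of 10%, 20% and 30% are 3, 6 and 9 patients. The rows with p0 = 0 or p1 = 0 are the worst case for that level of exposure. For cytokines the documents state neither the direction nor the size of a steroid effect, so for them the table shows only how imbalance turns into bias.

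**5. Which markers each exposure reaches.** On the protocol's own account, NSAIDs and coxibs reach prostaglandins, hence PGE2. No effect on Cathepsin G or the cytokines is stated. Whether the NSAID part applies at all depends on PGE2 being measured, and Section 3.2 names mPGES-1 in its place.

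**The case against.** **Medication is meant to be stable and is recorded.** Section 7.5 asks for unchanged drugs and doses, Section 7.5.1 for symptomatic therapy to be optimised early, Section 7.5.2 for contact with the centre before a new treatment, and Section 10.1 lists concomitant medication at each visit with these samples. A reader might infer that NSAIDs and coxibs are freely allowed; that goes too far. Stable use largely cancels within a patient. What stands is as-needed use: the contact rule is about safety, and a recorded drug without time of last intake does not show whether a given sample was affected.

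**Omega-3 and the wider immunology.** A reader might infer that omega-3 supplements contaminate the biomarkers, since the protocol says "the administration of omega-3 poly-unsaturated fatty acids lowers the expression of 5-LO". The inference fails: 5-LO is not a listed biomarker, and nothing links omega-3 to the markers that are. Nor does the text support an NSAID effect on the immunology results.

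**This belongs in an analysis plan.** Rules for leaving samples out may well stand there, and their absence here is no fault. But an analysis plan cannot move a sample drawn days after a steroid course or recover an intake time that was never asked for. Those are collection rules.

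**The remedy has a bias of its own.** Steroids follow relapses, so dropping post-steroid samples removes data from patients with active disease. The 28 days were set for MRI, and nothing shows that they suit cytokines or PGE2. Both points are fair. They favour delaying the draw over excluding it, and reporting all samples as well.

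**There may be a second off-drug sample.** Patients who stop at month 8 give one at month 12. That helps some patients, but month 12 has no post-steroid interval either.

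**Conclusion.** The concern holds in a limited form. As written, immunology and biomarker blood can be drawn within days of methylprednisolone while the MRI waits 28 days. Baseline is protected and there is no comparator, so a steroid effect can be read as immunomodulation by the study drug. As-needed NSAID or coxib use can shift PGE2 in either direction without being traceable to a sample.

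Illustrative false shifts run from a 24% fall to a 19% rise, and are nil when exposure is balanced. They rest on assumed exposure shares and an assumed 50% to 80% lowering. A steroid course ending at random during treatment has a 37.5% chance of falling within 28 days before a sample on the Section 10.1 schedule.

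A reader might infer that the efficacy conclusion is at risk. It is not: the MRI outcome has its own 28-day rule, and the safety assessments are not in question here. The affected measures are listed as tertiary in an open-label phase IIa study. Severity is minor; this is a cheap improvement.

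**What to change.** 1. **Steroids.** In Sections 7.5.3 and 10.1, apply the existing 28-day interval to immunology and biomarker blood by drawing it with the postponed MRI. If it is drawn earlier, flag the sample, leave it out of the main mechanism analysis and report an all-samples sensitivity analysis. The 28 days are carried over from MRI as a working choice and should be labelled so.
2. **NSAIDs.** At each biomarker visit, month 0 included, record the time of last NSAID, coxib or aspirin intake. Treat PGE2 samples taken within a pre-stated window after intake in the same way as early post-steroid samples.
3. **Analyte and schedule.** Reconcile PGE2 levels in the Summary with mPGES-1 serum levels in Section 3.2, and every-visit sampling in Section 3.2 with the shorter list in Section 10.1.

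No treatment is barred or changed; only sampling, recording and sample handling are affected.

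**Cost.** One or two case report form fields, one timing sentence and one analysis rule. A few samples will be delayed or left out, mostly from relapsing patients; the sensitivity analysis shows whether that matters.

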7.5.1 Symptomatic Therapies

Symptomatic therapy, such as treatment for spasticity, depression, bladder dysfunction, or fatigue is not restricted, but should be optimized as early as possible during screening/pre-treatment in an attempt to maintain consistent treatment for the duration of the study.

7.5.2 Therapies not allowed during Treatment

Any of the drugs mentioned in table 2 except corticosteroids are not allowed during the study participation. Before any treatment except the study drug is initiated, the patient or her/his outside physician should contact the study center to seek advice, if any safety issue might arise. This does not hold true for emergency cases.

7.5.3 Treatment of Relapses on Scheduled or Unscheduled Visits

Patients having a clinically significant relapse/exacerbation will be treated according to the recommendations of the German society for neurology (DGN) with 1000 mg methylprednisolone, given once a day via i.v. infusion for 3 days unless there are valid reasons for not treating or for alternative schedules. In case of a relapse each patient has to give written informed re-consent before continuing the study irrespective of his/her choice to receive methylprednisolone. In the case of methylprednisolone administration, a subsequent MRI examination will be postponed for at least 28 days, while treatment with BOSWELAN and study visits will be continued according to the study protocol.

7.5.4 Recording Concomitant Medication

Any medication and any non-drug procedure or therapy utilized from the start of study drug treatment until the completion of the study must be recorded in the subject's case report forms (CRFs) independent of the continuation of treatment with the study drug.

7.6 Treatment after study termination

Patients will be offered to visit the study centre in individually agreed intervals.

8. Schedule of Events, Tests, and Evaluations (see Study Flow Chart in the appendix)

Unless otherwise specified, the tests and evaluations described below for the screening visit must be performed within 7 days prior to the subject's first MRI in order to determine subject eligibility.

9. Efficacy Assessments

9.1 MRI Efficacy Assessments

See section 3.1 and 3.2

If a therapy with corticosteroids becomes necessary due to a relapse/exacerbation, the MRI has to be performed before the beginning of the corticosteroid therapy (but at least 28 days after the preceding MRI) or at least 28 days after the end of the corticosteroid therapy. The following MRIs have to be delayed accordingly.

10 SCHEDULE OF EVENTS

10.1 Tests and evaluations

Unless otherwise specified, tests and evaluations described below for the screening visit must be performed within seven days prior to the patient's first MRI. Blood samples should be drawn as early in the day as possible, preferably at the same time of day to avoid diurnal variation and before any steroids are taken in order to avoid depletion of lymphocytes by these agents.

In the event of an MS relapse, a MRI scan will be obtained prior to initiation of steroid therapy. The next scheduled MRI scan will be delayed until at least 28 days after the end of steroid therapy. Subsequent MRI scans will occur at regularly scheduled patient visits.

Additional non-pharmaceutical studies carried out at the discretion of the investigator when deemed appropriate for optimal management of the patient must also be reported.

See Study Schedule Flow Chart (App. A) for summary of tests and evaluations by time-point.

Month -3 (Screening Visit)

Unless otherwise specified, the tests and evaluations described below must be performed within seven days prior to the patient's first MRI in order to determine

patient eligibility:

- A complete medical history.
- A complete MS history.
- Inclusion and exclusion criteria.
- A complete physical examination.
- Vital signs and body weight.
- Haematology: see 11.3.
- Blood chemistries: see 11.3.
- Hepatitis B and C Screening or Check for recent Hepatitis B and C Screening: see 11.3.
- Urinalysis: see 11.3.
- Urine pregnancy test for women of child-bearing potential.
- Recording of concomitant medication.
- EDSS, SNRS, MSFC.
- HAQUAMS, MSIS29, HADS, Fatigue Severity Scale, HARAS for each Relapse within the last 12 months
- Cranial MRI.

Month -2 (\pm 7 days)

- Monitoring of adverse events.
- Vital signs and body weight.
- Urine pregnancy test for women of child-bearing potential.
- Recording of concomitant medication.
- Cranial MRI.
- EDSS, SNRS

Month -1 (\pm 7 days)

- Monitoring of adverse events.
- Vital signs and body weight.
- Urine pregnancy test for women of child-bearing potential.
- EDSS, SNRS, MSFC.
- Recording of concomitant medication.
- Cranial MRI.

Month 0 (\pm 7 days)

- Cranial MRI (within 7 days prior to study drug administration).
- Inclusion and exclusion criteria.
- Monitoring of adverse events.
- Complete physical examination.
- Vital signs and body weight.
- Urine pregnancy test for women of child-bearing potential.
- Haematology: see 11.3.
- Blood chemistries: see 11.3.
- Urinalysis: see 11.3.
- Immunological measures.
- Biomarker Assessment.
- EDSS, SNRS, MSFC.
- HAQUAMS, MSIS29, HADS, Fatigue Severity Scale
- Recording of concomitant medication

- Study drug administration followed by a 2 hour observation period

Day 1 (\pm 1 days)

- Monitoring of adverse events (Telephone call).

Day 4 (\pm 2 days)

- Monitoring of adverse events (Telephone call).

Day 13 (\pm 2 days)

- Monitoring of adverse events (Telephone call).

Month 1 (\pm 7 days)

- Monitoring of adverse events.
- Complete physical examination.
- Vital signs and body weight.
- Haematology: see 11.3.
- Blood chemistries: see 11.3.
- Urinalysis: see 11.3.
- Immunological measures.
- Biomarker Assessment.
- Urine pregnancy test for women of child-bearing potential.
- EDSS, SNRS, MSFC.
- HAQUAMS, MSIS29, HADS, Fatigue Severity Scale
- Recording of concomitant medication
- Study drug administration
- Cranial MRI.

Month 2 (\pm 7 days)

- Monitoring of adverse events.
- Complete physical examination.
- Vital signs and body weight.
- Haematology: see 11.3...
- Blood chemistries: see 11.3..
- Urinalysis: see 11.3..
- Urine pregnancy test for women of child-bearing potential.
- Recording of concomitant medication
- Cranial MRI.
- EDSS, SNRS

Month 3 (\pm 7 days)

- Monitoring of adverse events.
- Complete physical examination.
- Vital signs and body weight.
- Haematology: see 11.3.
- Blood chemistries: see 11.3..
- Urinalysis: see 11.3..
- Urine pregnancy test for women of child-bearing potential.
- Immunological measures.
- Biomarker Assessment.

- EDSS, SNRS, MSFC.
- HAQUAMS, MSIS29, HADS, Fatigue Severity Scale
- Recording of concomitant medication.
- Cranial MRI.

Month 4 (\pm 7 days)

- Monitoring of adverse events (Telephone call).
- EDSS (Telephone call)

Month 5 (\pm 7 days)

- Monitoring of adverse events.
- Vital signs and body weight.
- Haematology: see 11.3..
- Blood chemistries: see 11.3..
- Urinalysis: see 11.3..
- Urine pregnancy test for women of child-bearing potential.
- Recording of concomitant medication.
- Cranial MRI.
- EDSS, SNRS, MSFC.
- HAQUAMS, MSIS29, HADS, Fatigue Severity Scale

Month 6 (\pm 7 days)

- Monitoring of adverse events.
- A complete physical examination.
- Vital signs and body weight.
- Haematology: see 11.3..
- Blood chemistries: see 11.3..
- Urinalysis: see 11.3..
- Urine pregnancy test for women of child-bearing potential
- EDSS, SNRS, MSFC.
- HAQUAMS, MSIS29, HADS, Fatigue Severity Scale
- Recording of concomitant medication.
- Cranial MRI.

Month 7 (\pm 7 days)

- Monitoring of adverse events.
- Vital signs and body weight.
- Haematology: see 11.3..
- Blood chemistries: see 11.3..
- Urinalysis: see 11.3..
- Urine pregnancy test for women of child-bearing potential.
- EDSS, SNRS, MSFC.
- Recording of concomitant medication.
- Cranial MRI.

Month 8 (\pm 7 days)

- Monitoring of adverse events.
- A complete physical examination.
- Vital signs and body weight.
- Haematology: see 11.3..

- Blood chemistries: see 11.3..
- Urinalysis: see 11.3..
- Urine pregnancy test for women of child-bearing potential.
- Immunological measures.
- Biomarker Assessment.
- EDSS, SNRS, MSFC,
- HAQUAMS, MSIS29, UNDS.
- Recording of concomitant medication.
- Cranial MRI.

* Optional for patients choosing to continue treatment with BOSWELAN:

- **Month 9 (\pm 7 days) ***
 - Monitoring of adverse events (Telephone call)
 - EDSS (Telephone call)
- **Month 10 (\pm 7 days) ***
 - Monitoring of adverse events (Telephone call).
 - EDSS (Telephone call)
- **Month 11 (\pm 7 days) ***
 - Monitoring of adverse events (Telephone call).
 - EDSS (Telephone call)

Extension: Month 12 (\pm 7 days) / Early Termination

- Monitoring of adverse events.
- A complete physical examination.
- Vital signs and body weight.
- Haematology: see 11.3..
- Blood chemistries: see 11.3..
- Urinalysis: see 11.3..
- Urine pregnancy test for women of child-bearing potential.
- Immunological measures.
- Biomarker Assessment.
- EDSS, SNRS, MSFC.
- HAQUAMS, MSIS29, HADS, Fatigue Severity Scale
- Recording of concomitant medication.
- Cranial MRI.

Unscheduled Visits / Relapse

In case of Relapse mandatory

- Monitoring of adverse events.

- Vital signs and body weight
- Recording of concomitant medication.
- Cranial MRI
- EDSS, SNRS, MSFC.
- HAQUAMS, MSIS29, HADS, Fatigue Severity Scale
- HARAS
- Other procedures as indicated by the investigator

Relapse follow-up

- Monitoring of adverse events.
- Vital signs and body weight
- Recording of concomitant medication.
- EDSS, SNRS, MSFC.
- HAQUAMS, MSIS29, HADS, Fatigue Severity Scale
- HARAS
- Other procedures as indicated by the investigator

All other unscheduled visits including unscheduled drug dispensation

- Monitoring of adverse events.
- Recording of concomitant medication.
- Other procedures as indicated by the investigator

11. Safety Assessments

